7.3. Justification for the Study Design

Artificial urinary sphincters are considered the gold standard for the treatment of moderate to severe post-prostatectomy SUI.^{4,5,2,6} With a single arm study design, all subjects receive the standard of care procedure.

8. Subject Selection

8.1. Study Population and Eligibility

This study will enroll adult males with moderate to severe primary stress urinary incontinence (as assessed by a baseline pad weight test) due to ISD who meet the indications for surgical correction of urinary incontinence.

To assess for eligibility for this study, inclusion and exclusion criteria are included in Sections 8.2 and 8.3 below.

8.3. Exclusion Criteria

Subjects who meet any one of the following criteria (Error! Reference source not found.) cannot be included in this study and will be excluded from this clinical study.

Table 8.3-1: Exclusion Criteria

Exclusion Criteria

- 1. Previously had or currently has a device implanted (AUS/Sling, or otherwise) for treatment of SUI or urge incontinence
- 2. Primary urgency incontinence
- 3. Postvoid residual volume greater that 150 ml or a history of difficulty emptying the bladder
- 4. Recurrent vesicourethral anastomotic stricture or urethral stricture disease within the past 6 months
- 5. Known urogenital malignancy other than previously treated prostate cancer
- 6. Recurrent prostate cancer that is expected to require intervention during the study follow-up period
- 7. History of recurrent bladder stones within the past 12 months prior to signing the informed consent
- 8. Neurogenic bladder
- 9. Need for intermittent catheterization
- 10. Known history of untreated/uncontrolled bleeding diathesis or coagulopathy
- 11. Immunosuppressed or on medical therapy which would impact the immune system
- 12. Uncontrolled diabetes, defined as (HbA1c>10)
- 13. Has a genitourinary mechanical prosthesis that was implanted within 3 months from the date of consent
- 14. Had a post-implantation infection associated with the device after genitourinary mechanical prosthesis was implanted
- 15. Undergone bulking procedure within 6 months of the baseline assessment
- Poor candidate for surgical procedures and/or anesthesia due to physical or mental conditions
- 17. Urinary incontinence due to or complicated by an irreversibly obstructed lower urinary tract
- 18. Irresolvable detrusor hyperreflexia or bladder instability
- 19. Currently enrolled or plans to enroll in another device or drug clinical trial
- 20. Currently using an indwelling catheter or condom catheter for treatment of incontinence and is not willing to discontinue use at least 4 weeks prior to baseline assessment
- 21. Known allergy or sensitivity to rifampin or to minocycline HCl or other tetracyclines (only applicable when implanting with InhibiZone version of this device)
- 22. Systemic lupus erythematosus because minocycline HCl has been reported to aggravate this condition (only applicable when implanting with InhibiZone version of this device)

9. Subject Accountability

9.1. Point of Enrollment

Subjects will be considered enrolled in the study once they sign the informed consent. All enrolled subjects will have been consented prior to the procedure. All enrolled subjects with a surgery initiated (i.e. first incision) will be considered part of the Intent-to-Treat (ITT) population.

9.2. Withdrawal

All subjects enrolled in the clinical study (including those withdrawn from the clinical study) shall be accounted for and documented. If a subject withdraws from the clinical investigation, the reason(s) shall be reported. If such withdrawal is due to problems related to device safety or performance, the investigator shall ask for the subject's permission to follow his/her status/condition outside of the clinical study.

Reasons for withdrawal include but are not limited to physician discretion and subject choice to withdraw consent. While study withdrawal is discouraged, subjects may withdraw from the study at any time, with or without reason, and without prejudice to further treatment. All applicable electronic Case Report Forms (eCRFs) up to the point of subject withdrawal and an End of Study eCRF must be completed. Additional data may no longer be collected after the point at which a subject has been withdrawn from the study or withdraws his/her consent. Data collected up to the point of subject withdrawal may be used for study analysis, unless local regulations specify differently.

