9.2.2. Involuntary Withdrawal

Subjects may be involuntarily withdrawn from the study if the Investigator determines it is in the subject's best interest. If the subject is withdrawn at the investigator's discretion, the reason for withdrawal must be documented in the subject's medical records.

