11.1.1.1. Hypotheses

The study will evaluate whether the proportion of subjects experiencing a treatment success exceeds 65% at 12 months. The null and alternative hypotheses for this evaluation are

H₀: $p \le 65\%$ H₁: p > 65%

where p is the proportion of subjects who are a treatment success at 12 months.

11.1.1.2. Sample Size

The sample size calculation is based on an assumption that the treatment success rate is 80%⁴. With a one-sided type I error of 0.025 and a type II error of 0.10 (90% power), a sample size of 96 subjects are needed to demonstrate the proportion of subjects who are a treatment success exceeds 65%. Assuming a 20% attrition rate, at least 120 subjects with AMS 800 AUS procedure are required.

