11.1.1.3. Statistical Methods

The hypotheses will be evaluated using a one-sided exact binomial test. In addition, a two-sided 95% exact (Clopper-Pearson) confidence interval will be presented. Sensitivity analysis to missing data will be performed using tipping-point analysis. If a medical revision is performed due to efficacy reasons at or prior to the 12 month visit, then the subject is considered as experiencing a treatment failure.

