11.3. Data Analyses

The analyses will include only the available cases unless specified otherwise. Presentation of summary statistics for continuous variables will include N, mean, median, standard deviation, minimum, and maximum values. For categorical variables, the number and percentage under each category will be presented.

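### An activated man who withdraws because the device does not work, without an efficacy revision, drops out of the primary test instead of counting as a failure, which biases the success rate upward against the 65% goal

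*Combined protocol and SAP*

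**What the plan says.** Section 9.2 of the protocol requires the reason for any withdrawal to be reported. It names one class of reason explicitly, in a clause that begins "If such withdrawal is due to problems related to device safety or performance" and has the investigator ask permission to follow the man outside the study. It also says that data collection may stop at withdrawal. Section 9.2.2 adds withdrawal by the investigator: "Subjects may be involuntarily withdrawn from the study if the Investigator determines it is in the subject's best interest", again with the reason documented.

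Section 11.1.1.3 has one rule that turns an event into a failure: "If a medical revision is performed due to efficacy reasons at or prior to the 12 month visit", the man is a treatment failure. The only provision there for missing data is a tipping-point sensitivity analysis, which Section 11.2.1 repeats. Section 11.2 names the ITT population (first incision) for the endpoint analyses but gives no imputation. The default in Section 11.3 is "The analyses will include only the available cases unless specified otherwise".

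Section 11.1.1.2 fits this reading: "a sample size of 96 subjects are needed to demonstrate the proportion of subjects who are a treatment success exceeds 65"%, raised to 120 treated for 20% attrition. Men without a Month 12 result are planned out of the denominator.

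**The concern.** Take two activated men for whom the sphincter does not control leakage. One has a revision for that reason and is a failure. The other declines further surgery and withdraws, and lack of effect is recorded as his reason. He has no Month 12 pad test, no rule scores him, and the available-case default removes him from numerator and denominator alike. The scoring turns on whether he accepted a second operation, not on whether the device worked.

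The trial has one arm and a fixed goal, so no comparator loses men in the same way. Removing probable non-responders can only raise the observed success rate. Section 11.2.1 presents the exact binomial test as conservative against bias toward meeting the goal. Exactness protects against approximation error, not against selective loss of failures.

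**Working it through.** **Inputs from the documents.** Performance goal 65% (Section 11.1.1.1: "The study will evaluate whether the proportion of subjects experiencing a treatment success exceeds 65% at 12 months"); assumed success 80%, one-sided alpha 0.025, 90% power, 96 evaluable, 20% attrition and 120 treated (Section 11.1.1.2); one-sided exact binomial test (Section 11.1.1.3).

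**Reproducing the plan's figure.** At n=96 the smallest r with P(X≥r | 0.65) ≤ 0.025 is 72. The exact type I error is 0.0236 and power at 0.80 is 0.909; at n=95 power is 0.874. Then 96/(1−0.20) = 120. The stated figures reproduce.

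**Assumptions not in the documents.** The plan gives no rate of device-related withdrawal. I take 120 treated men and 24 missing, of whom d withdrew for device performance or lack of effect without an efficacy revision. The other 24−d are missing at random. True success over all 120 is 65%, the edge of the null.

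**Formulas.** If a share s of the d men would have succeeded, the success rate among the analysed men is q = (0.65 − s·d/120)/(1 − d/120). The type I error of the available-case test is P(X≥72 | n=96, q). Example, d=6 and s=0: q = 0.65/0.95 = 0.6842, giving 0.0991. With s=0.30: q = (0.65 − 0.015)/0.95 = 0.6684, giving 0.0535.

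| d | % of 120 | q (s=0) | Type I error, s=0 | Ratio to 0.0236 | Type I error, s=0.30 |
|---|---|---|---|---|---|
| 0 | 0 | 0.6500 | 0.0236 | 1.0 | 0.0236 |
| 1 | 0.8 | 0.6555 | 0.0304 | 1.3 | 0.0271 |
| 2 | 1.7 | 0.6610 | 0.0390 | 1.7 | 0.0311 |
| 3 | 2.5 | 0.6667 | 0.0497 | 2.1 | 0.0356 |
| 4 | 3.3 | 0.6724 | 0.0630 | 2.7 | 0.0408 |
| 6 | 5.0 | 0.6842 | 0.0991 | 4.2 | 0.0535 |

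A result at the boundary is fragile: 72/96 passes, but one added failure gives 72/97 with p=0.034, which does not.

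**With the d men counted as failures.** The denominator becomes 96+d with its own exact critical value. Type I error is P(X≥r | 96, q), because the d men contribute no successes. Power is shown two ways: with 80% success over all 120 men (completers' rate 0.80/(1−d/120), for example 0.8205 at d=3 and 0.8421 at d=6), and with 80% among completers only (overall rate 0.80×117/120 = 0.78 at d=3 and 0.80×114/120 = 0.76 at d=6).

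| d | Rule | Type I error | Power, 80% over all 120 | Power, 80% among completers |
|---|---|---|---|---|
| 1 | ≥73/97 | 0.018 | 0.897 | 0.863 |
| 2 | ≥74/98 | 0.013 | 0.884 | 0.802 |
| 3 | ≥74/99 | 0.018 | 0.916 | 0.802 |
| 4 | ≥75/100 | 0.013 | 0.906 | 0.727 |
| 6 | ≥77/102 | 0.007 | 0.886 | 0.541 |

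The rule keeps type I error below 0.025 throughout. It is somewhat conservative while other men remain missing: at d=6 the failures weigh 6/102 = 5.9% of the analysed set, against 6/120 = 5.0% of those treated.

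**The case against.** **A safety problem is not a failure under this protocol.** This stands. Section 11.1.1.3 confines failure to revisions for efficacy reasons. Section 10.11 lists infection, erosion and mechanical malfunction as reasons for revision and sends revised men back to their next regular visit. A reader might infer that every withdrawal for device safety or performance is a failure by the protocol's own logic. The documents support that only for lack of effect or poor performance. Extending it to safety would create a new composite, under which a man revised for infection who stays is judged on pad weight while one who leaves for infection fails automatically.

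**The tipping-point analysis covers it.** Partly. It can show how many missing men must be failures to overturn the result. It is a sensitivity analysis with no stated decision rule, so the primary conclusion does not depend on it. A reader might infer that it ignores the recorded reason, but the documents do not describe its mechanics and so do not establish that.

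**The group is narrow and its size unknown.** This also stands. Section 10.11 counts removal of components within medical revision, so a man explanted for lack of effect before leaving appears to be a failure already. Remote visits, mailed pads and a three-month window either side of Month 12 should limit losses. The Section 9.2 clause on device-related withdrawal deletes nobody: the deletion follows from Sections 11.3 and 11.1.1.2. A reader might infer a several-fold rise in false positives as the expected outcome. That needs roughly 4 to 6 such men, nearly all failures; with 1 or 2 the rise is 1.3 to 1.7 times.

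**Conclusion.** The point holds for withdrawals after activation for lack of effect or a device performance problem, without an efficacy revision. As written, the plan leaves these men out of the primary test although their reason is reported, and the bias runs toward meeting the goal. Type I error is 0.030, 0.039, 0.050, 0.063 and 0.099 at d=1, 2, 3, 4 and 6, against 0.024 with none, and 0.054 at d=6 if 30% of them would have succeeded. These values rest on 24 of 120 men missing, the others missing at random, and an assumed d for which the documents give no rate.

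Nor should the repair be read as free of any cost in power. Power near 0.90 requires 80% success over all 120 men. The documents do not say whether their 80% assumption includes men who leave for lack of effect.

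**What to change.** Add to Section 11.1.1.3: an ITT subject who withdraws or is withdrawn after activation and before the Month 12 pad test, with lack of effect or a device performance problem as the recorded reason, is a treatment failure and stays in the denominator. Make sure the End of Study eCRF can identify that reason; it may already do so, since the form is not shown.

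Keep withdrawals for device safety reasons alone in the tipping-point analysis, and also present the primary result with them counted as failures.

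State which men the 80% assumption covers and restate power: 0.89 to 0.92 across d=3, 4 and 6 if it holds over all 120, but about 0.80 (d=3) and 0.54 (d=6) if it holds only among completers.

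The cost is a short SAP amendment, which Section 11.3.6 allows before the analyses are performed, a somewhat less favourable success rate, and possibly a larger sample if the completers-only reading of 80% is the intended one. The rule also depends on the recorded reason, and Section 9.2 lets a man leave without giving one, so men with no reason stay with the other missing data.

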9.2.1. Voluntary Withdrawal

Subjects may withdraw from the study at any time. At the time of withdrawal, the Investigator shall document the reason for the withdrawal. For subjects who withdraw from the study and decide to revoke their authorization to use and disclose their medical information, the information that has already been collected in the study record may continue to be used; however, no new information will be obtained or added.

9.2.2. Involuntary Withdrawal

Subjects may be involuntarily withdrawn from the study if the Investigator determines it is in the subject's best interest. If the subject is withdrawn at the investigator's discretion, the reason for withdrawal must be documented in the subject's medical records.

9.3. Lost to Follow-Up

If a participant fails to contact the clinic for a required study visit, the site will attempt to contact the participant and reschedule the missed visit prior to the next visit window, and are encouraged to remind the participant on the importance of maintaining the assigned visit schedule and ascertain if the participant wishes to and/or should continue in the study.

Before the subject may be considered lost to follow-up, the investigator must make the following attempts to contact the subject:

- Three documented telephone attempts
- One certified letter

If the subject can be reached and no longer wishes to participate in the study, the Investigator shall document the reason for the withdrawal and complete the End of Study eCRF.

If subject is not able to be reached after the required attempts to contact the subject have been made and the subject has missed two consecutive follow-up visits within the 12-month follow-up schedule, or the subject has missed the final 12-month follow-up visit, the subject may be considered lost to follow-up. The Investigator should document in the subject's medical record the attempts to contact the subject and the reason for withdrawal.

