10.1. Data Collection

The data collection schedule is shown in Table 10.1-1. All study data will be recorded on source documentation and captured within Case Report Forms (CRFs) for the purposes of this study. Study data will be monitored by Boston Scientific or representatives and as applicable on a regular basis as outlined in the study Monitoring Plan.

Table 10.1-1: Data Collection Schedule

Procedure/Assessment	Screening / Enrollment Visit²	Pre-Operative / Baseline Visit (≤90 calendar days before index procedure)	Index Procedure (≤90 calendar days from screening visit)	Device Activation (30-45 calendar days post index procedure)	Follow-up Visits ⁴		
					3 Month Visit ⁵ (±6 Weeks)	6 Month Visit ⁵ (± 3 Months)	12 Month Visit ⁵ (± 3 Months)
Informed consent process, including informed consent signature and date	X						
Inclusion/Exclusion Criteria Review	X	X					
Demographics		X					
Physical assessment, including weight and height		X				X^6	X^6
Medical history ¹	X	X					
3-day eDiary		X				X	X
24-hour Pad Weight Test		X		X		X	X
# Pads per Day		X			X	X	X
IQoL (Urinary Incontinence Quality of Life)		X			X	X	X
IIQ-7 (Incontinence Impact Questionnaire)		X			X	X	X
EQ-5D (Health Status)		X					X
Patient Ease of Use Questionnaire						X	X
Index Procedure			X				
Assessment of Adverse Events and Device Deficiencies ³			X	X	X	X	X
End of Study							X

¹Medical History at baseline includes documented absence of urine culture.

²The Screening/Enrollment Visit and Pre-Operative/Baseline Visit may be combined and occur up to 90 calendar days prior to the study procedure with confirmed absence of infection.

³Reportable events include (procedure related) AEs, SAEs, SADEs, ADEs and device deficiencies. Adverse events that are not related to the device and not related to the procedure will not be collected; however, these assessments should be noted in the subject's medical records.

⁴Every effort should be made to do the follow-up visit within the window; however, if this is not possible, the site should attempt to complete the visit as soon as possible, but before the next visit window opens. Follow-up visits will be considered missed once the visit window for the next follow-up visit opens. For the Month 12 visit, the visit is not considered missed until the last day of the visit window. All follow-up visit windows start from the day of device activation.

₅Visits may be conducted in clinic or remote.

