10.9. Months 6 [\pm 3 Months] and 12 Visit [\pm 3 Months]

The 6-month follow-up visit occurs 180 calendar days after the day of device activation, \pm 3 months. The 12-month follow-up visit occurs 365 calendar days after the day of device activation, \pm 3 months. These visits may occur either remotely or in clinic.

Questionnaires cannot be completed over the phone. The site must mail the questionnaires to the subjects and the subjects should return the questionnaires to the site as soon as possible. Pads can be mailed to subjects and returned per the pad weight protocol or dropped off by the subject.

The following data will be collected at the 6-month and 12-month visits:

- Physical examination including height and weight (Note: If a remote visit is completed, the subject may self report his height and weight.)
- 3-day eDiary
- 24-hour pad weight test
- Number of pads per day
- IQoL
- IIQ-7

- EQ-5D (Month 12 only)
- Patient Ease of Use
- Assessment of adverse events and device deficiencies
- Study completion (12-month follow-up only)

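### Section 9.3 permits a site to close an unreachable man who missed Months 3 and 6 just as the Month 12 window opens, with about 180 days left to collect the primary outcome

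*Combined protocol and SAP*

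**What the plan says.** Section 9.3 sets a joint condition. The first part is unreachability: "If subject is not able to be reached after the required attempts to contact the subject have been made". The required attempts are "Three documented telephone attempts" and one certified letter. The second part is that "the subject has missed two consecutive follow-up visits within the 12-month follow-up schedule"; a missed Month 12 visit serves equally well as the second part. A man who meets both parts may, at the site's choice, be given the status. For such a man the investigator documents the attempts and why he was withdrawn. For any missed visit, "the site will attempt to contact the participant and reschedule the missed visit prior to the next visit window".

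Table 10.1-1 (footnote 4) and Section 10.7 define a missed visit: "Follow-up visits will be considered missed once the visit window for the next follow-up visit opens". Month 12 is the exception; it is not missed until its window's last day.

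On timing, Section 10.9 says "The 12-month follow-up visit occurs 365 calendar days after the day of device activation", with a margin of 3 months either side. The visit may be remote and pads may be mailed. The only scheduled follow-up visits are Months 3, 6 and 12.

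Section 9.2 rules out further data collection once a man has been withdrawn. On analysis, Section 11.3 says "The analyses will include only the available cases unless specified otherwise". Sections 11.1.1.3 and 11.2.1 add a tipping-point analysis for missing primary outcomes.

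**The concern.** The two visits that can trigger early closure do not carry the primary endpoint. Month 3 has no pad-weight test, and the Month 6 test is a secondary endpoint. The branch can nevertheless be used to close a man's record before the Month 12 test, which does carry it, has fallen due.

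What is at stake is bias more than precision. This is a single-arm comparison with a fixed 65% goal, analysed on available cases, so no control arm offsets selective loss. If men who stop responding do worse than men who stay, leaving them out raises the observed success rate. The documents do not say whether they do worse. Collecting the outcome is the only remedy that does not depend on assuming an answer.

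**Working it through.** **Sample size, reproduced first.** Inputs from Section 11.1.1.2: null rate 0.65, assumed rate 0.80, one-sided alpha 0.025, 90% power, 20% attrition. Take the smallest r with P(X ≥ r | n, 0.65) ≤ 0.025; power is P(X ≥ r | n, 0.80).

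- n = 96: r = 72, actual alpha 0.0236, power 0.909.
- 96 / (1 − 0.20) = 120 with procedure, so 120 − 96 = 24 losses are budgeted.

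The plan's figures are confirmed and do not depend on this point.

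**Which pair of visits matters.** With visits at Months 3, 6 and 12, the consecutive pairs are (3, 6) and (6, 12). The second pair includes a missed Month 12 visit, which is sufficient by itself. The two-visit branch therefore adds something only through (3, 6).

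**When it is met.** Days count from activation. The protocol gives targets of day 90, 180 and 365 and margins of 6 weeks, 3 months and 3 months. I take 3 months as 90 days.

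| Visit | Window |
|---|---|
| Month 3 | 90 ± 42 = day 48 to 132 |
| Month 6 | 180 ± 90 = day 90 to 270 |
| Month 12 | 365 ± 90 = day 275 to 455 |

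- Month 6 counts as missed when the Month 12 window opens, at day 275.
- Time to the Month 12 target: 365 − 275 = 90 days.
- Time to the end of the window: 455 − 275 = 180 days.
- With 3 months as 91 to 91.3 days, the window is about day 274 to 456, leaving 182 to 183 days.
- The Synopsis puts participant duration at 13.5 months for a man seen at the end of his window. That fits 12 + 1.5 months, not 12 + 3. On a 6-week margin the window would be day 323 to 407, leaving 84 days. I use the 3 months given in Table 10.1-1 and Section 10.9.

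**Where the contact attempts fall.** The calls and letter carry no date, and rescheduling effort is directed to the time before the next window. All four attempts can be finished before day 275, with none inside the Month 12 window.

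**A related inconsistency.** The Month 6 window opens at day 90. By the missed-visit rule, Month 3 then counts as missed on its own target day, although its window runs to day 132. This makes the first of the two misses easier to record.

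**Size.** Each unmeasured man widens the range of possible success proportions among 120 men by 1/120 = 0.83 percentage points. The documents do not give the number affected. If it were 2 to 4 (an assumption), the range would widen by 2/120 = 1.7 to 4/120 = 3.3 points.

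**The case against.** A reader might infer that two missed visits alone are enough to exit a man. They are not: the same sentence also requires that three calls and a certified letter have failed. A man who can be reached stays in unless he declines. This stands, and it lowers the yield of any fix, because many unreachable men will not return a pad kit. It does not close the gap, because a man not reached before day 275 may still be reached in the following six months and nothing requires a site to try.

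The rule is also permissive, and Section 9.3 does not say that contact ends. The bar on further data sits under withdrawal in Section 9.2. Other text leans towards continued follow-up: Section 7 follows men to Month 12, study completion or discontinuation; Section 9.4 keeps intent-to-treat men on the visit schedule; and Section 10.7 urges sites to complete visits. This stands too. The link to Section 9.2 is an inference from Section 9.3 recording such men as withdrawn. It is a reasonable reading for a site, and with up to 30 sites it may be applied unevenly.

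A reader might also infer that these losses take the trial below 90% power. The documents do not support that. The men fall within the 24 budgeted losses, and 120 is a minimum. Exact power is also sawtoothed: 0.909 at n = 96, 0.896 at 93 and 0.857 at 92, but also 0.8998 at 97 and 0.890 at 98. Small differences around 96 mostly reflect discreteness.

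Finally, the tipping-point analysis addresses this kind of missingness. It shows how far the result depends on the missing men, but it recovers no outcomes.

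**Conclusion.** The point holds in a limited form. Section 9.3 permits, but does not require, closing an unreachable man at about day 275, with about 180 days of the primary-endpoint window unused and no attempt required within it. The branch that allows this has no separate function, since the Month 12 branch closes the same men at the end of the window.

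The timing rests on reading 3 months as 90 days and on the window in Table 10.1-1 and Section 10.9. That closure ends pursuit of the outcome is an inference from Sections 9.3 and 9.2 read together. The consequence is potentially avoidable missing primary outcomes in an available-case analysis. The number of men is unknown and probably small, the direction of any bias is not known, and no power loss is claimed. This is a cheap improvement of low severity.

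**What to change.** In Section 9.3, delete the two-consecutive-visit branch, or state that meeting it does not end attempts at Month 12. Allow lost-to-follow-up status only after the Month 12 window has closed without a visit. Require the three calls and the certified letter to be made, or repeated, inside that window, with the mailed 24-hour pad kit offered. In the same edit, reconcile the missed-visit rule with the Month 3 window, and the Synopsis participant duration with the Month 12 window.

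The cost is about one sentence for the main change, a few extra calls and mailings, and later close-out for a few men. The sample size stays at 96 evaluable and 120 with procedure.
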